8.4 Cost-Utility Analysis (CUA)

Quality Adjusted Life Years (QALY) will be measured with the HUI3. QALY is an important component of Cost-Utility Analysis (CUA), a variant of Cost-Effectiveness Analysis (CEA); therefore, we will be able to calculate incremental cost per QALY gained between the two treatments. Of the available utility scales, the HUI3 is the most powerful as it can discriminate among close to one million different health states. Utility scores of HRQL derived from responses to the HUI3 questionnaire have the required measurement properties for calculating QALYs[18].

The methodology used for data analysis will be as per Drummond et al. Methods for the economic evaluation of health care programs, Oxford University Press, 2005 [23] and Thoma et al. A methodological guide to performing cost-utility study comparing surgical techniques, Can J Plast Surg 2004;12:179-187[18] and Thoma et al. Cost-Effectiveness Analysis Parallel to a Randomized Controlled Trial Comparing Vertical Scar Reduction and Inverted T-Shaped Reduction Mammoplasty PRS 134:1093, 2014[24].

Probabilistic sensitivity analysis will be undertaken to assess stochastic uncertainty using nonparametric bootstrapping to quantify the joined effect of uncertainty around the costs and the QALYs. Nonparametric bootstrapping will be used to estimate the confidence interval around the mean treatment effects and the incremental cost-effectiveness ratio[30]. This technique randomly draws with replacement samples of the original cost and quality-adjusted life-year data over a large number of times (1000 replications) [23]. These bootstrapped cost-QALY pairs are graphically represented on an incremental cost-effectiveness plane. The bootstrapped estimates will be further used to construct the cost-effectiveness acceptability curves. These will show the probability that collagenase injection is cost-effective compared to limited palmar fasciectomy across a selected set of cost-effectiveness threshold values when taking into consideration the uncertainty inherent in the estimates[31].

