3.3 Secondary Outcome Measures

Secondary outcomes include:

- (a) HRQL measured with the Health Utility Index Mark 3 (HUI3), a generic multi-attribute health-status classification instrument [15].
- (b) HRQL measured with the Unité Rhumatologique des Affections de la Main (URAM), a disease-specific HRQL measure developed for Dupuytren's contracture [16].
- (c) HRQL measured with the Southampton Dupuytren's Scoring Scheme (SDSS), a disease-specific scoring system developed for Dupuytren's contracture [17].
- (d) Quality Adjusted Life Years (QALY) measured with the HUI3. QALY is an important component of Cost-Utility Analysis (CUA), a variant of Cost-Effectiveness Analysis

(CEA); therefore, we will be able to calculate incremental cost per QALY gained between the two treatments. Utility scores of HRQL derived from responses to the HUI3 questionnaire have the required measurement properties for calculating QALYs[18].

- (e) Self-reported healthcare utilization (e.g. visits to hand surgeons, family physician, parking costs, etc.) and productivity loss (e.g. time lost from work and leisure activities by patient and caregiver).
- (f) Range of motion (ROM) of hand joints measured with goniometry
- (g) Recurrence rates defined as an increase in joint contracture in any treated joint of at least 20 degrees at one year post-treatment.
- (h) Necessary Dupuytren's Disease treatments applied to the previously affected digit(s) (the digit(s) treated in the EXTEND trial) up to 4 years following their original (EXTEND trial) treatment.

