6.2 Baseline Assessment

Baseline demographic information will be collected approximately 1 week prior to the patient's procedure and will include age, height, weight, marital and employment status, income and education level, medical history and level of co-morbidities. ROM will also be collected.

In addition, 4 HRQL questionnaires will be administered at the baseline visit: MHQ, HUI3, URAM, and SDSS (see Health-related Quality of Life section below for further details). These questionnaires will be completed in the office/clinic and will take approximately 20-30 minutes to complete. The patient will also be given a diary to keep track of hospital and doctor visits, blood work, medications, and other health services related to their procedure as well as personal expenses incurred and time off from work.

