8 STATISTICAL CONSIDERATIONS

8.1 General

Analysis of baseline characteristics will be performed using descriptive statistics reported by group as mean (standard deviation [SD]) or median (first quartile, third

quartile) for continuous variables and count (percent) for categorical variables. All analyses of primary and secondary outcomes will follow the intention-to-treat principles. We will use multiple imputation to handle missing data [25]. The results for comparisons between groups will be presented as mean difference (for continuous outcomes) and relative risk (for binary outcomes), corresponding 95% confidence intervals and associated p-values. P-values will be reported to four decimal places with p-values less than 0.001 reported as $p < 0.001$. All analyses will be performed using SAS software version 9.4 (Cary, NC, USA).

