8.2 Sample Size Determination

The sample size will be based on the 12 month post-randomization MHQ score adjusted for baseline MHQ score. According to the paper by London, Stepan and Calfee [26] the MCID for the total MHQ score from an ROC analysis of patients from a population with multiple hand and forearm diagnoses is 8.7. The MCID for the total MHQ score falls between 8-13 points (depending on the method used to obtain an MCID) with a mean equal to 10.8. If we adopt an MCID of 8.7 it will be in the lower end of the range of estimates which will require a larger sample size than if the MCID were larger. For an estimate of the SD of the total MHQ score for patients with DD we obtain a value of 15.0 from the one week pre-operative assessment and 16.0 for the 12 month post-operative assessment based on the papers by Thoma et al [27,28]. The midpoint of these two estimates is 15.5.

If we use $\alpha=0.05$, $\beta = 0.80$, $MCID=8.7$ and $SD=15.5$ for the sample size calculation, assuming a correlation value of 0.0 between baseline and 12-month post-randomization MHQ scores, based on the method outlined in Borm et al[29] the required total sample is 102 patients, or 51 per group. If we account for a 20% loss to follow-up rate the required sample increases to 128 (64 per group). These calculations assume that the relationship between the baseline and 12 month post-randomization MHQ scores is linear and that the slopes of the best fit lines of the two groups are parallel.

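### Section 8.4 plans a bootstrap interval on the ICER that cannot be read as a range of cost per QALY if QALY differences straddle zero; net benefit with an interval, from the same replicates, is a cheap improvement

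*Combined protocol and SAP*

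**What the plan says.** Cost-effectiveness from the patient, payer and societal perspectives is a secondary objective (Section 2.2). Section 3.3 promises the ratio itself: "we will be able to calculate incremental cost per QALY gained between the two treatments".

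Section 8.4 sets out the uncertainty analysis. It draws 1000 bootstrap replicates of the cost and QALY data. On intervals it says: "Nonparametric bootstrapping will be used to estimate the confidence interval around the mean treatment effects and the incremental cost-effectiveness ratio", with a citation to reference 30. The replicate pairs are plotted on the cost-effectiveness plane and feed acceptability curves "across a selected set of cost-effectiveness threshold values"; the values are not listed. No net-benefit estimate or interval is named. Further method detail is deferred: "The methodology used for data analysis will be as per" three cited sources (references 18, 23 and 24).

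On baseline utility, Section 6.2 states: "4 HRQL questionnaires will be administered at the baseline visit: MHQ, HUI3, URAM, and SDSS". Section 8.4 mentions no adjustment of QALYs for it. Randomization is stratified by primary joint type (Section 4.5.1).

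**The concern.** The ICER is a ratio whose sign and size do not order outcomes. A positive value can mean that collagenase costs more and gives more QALYs, or that it costs less and gives fewer. A negative value can mean that it dominates or is dominated. The ratio also runs to plus or minus infinity as the QALY difference approaches zero. While all replicates share one sign of the QALY difference, sorting the ratios and taking percentiles gives a readable range. Once they lie on both sides of zero, the sorted list mixes opposite conclusions and its end points have no meaning as cost per QALY.

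The trial was sized for the MHQ, not for QALYs, so a QALY difference that is not clearly separated from zero is a realistic outcome. The one planned interval that combines cost and QALYs would then be the one a reader cannot use.

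**Working it through.** **1. The plan's own figure.** Section 8.2 gives 51 evaluable patients per group (alpha 0.05, MHQ difference 8.7, SD 15.5, correlation 0; the printed β of 0.80 has to be read as power). By the normal formula, 2 × (1.96 + 0.8416)² × 15.5² / 8.7² = 49.8; the t-based version gives 50.8, so 51. Then 102 / 0.80 = 127.5, so 128 in total or 64 per group. The stated size reproduces. I use 51 and 64 per arm below.

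**2. Assumptions.** The documents give no HUI3 SD, HUI3 correlation or expected QALY difference. I assume:
- trapezoid QALYs over the HUI3 visits at 0, 1, 3, 6 and 12 months (visit times from Sections 6.2 and 6.3), which gives weights 1/24, 3/24, 5/24, 9/24 and 6/24;
- HUI3 SD 0.15-0.25;
- baseline-to-follow-up correlation rb 0.3-0.7;
- correlation among follow-up visits rf from rb up to 0.8.

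**3. Standard error of the unadjusted QALY difference.** SE = SD × √(w′Rw) × √(2/n), where w holds the weights and R the correlations.
- Smallest (SD 0.15, rb = rf = 0.3, n = 64): Σw² = 152/576 = 0.264; w′Rw = 0.3 + 0.7 × 0.264 = 0.485; SE = 0.15 × 0.696 × 0.177 = 0.0185.
- Largest (SD 0.25, rb 0.7, rf 0.8, n = 51): w′Rw = 0.845; SE = 0.25 × 0.919 × 0.198 = 0.0455.

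**4. How often replicates straddle zero.** Define straddling as more than 2.5% of replicates on each side. This happens when the observed difference is below 1.96 × SE, that is 0.036 to 0.089 QALY. For a true difference d, P = Φ(1.96 − d/SE) − Φ(−1.96 − d/SE). The central case is SD 0.20, rb 0.5, rf 0.65.

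| True difference (QALY) | Smallest SE | Central, n = 64 | Central, n = 51 | Largest SE |
|---|---|---|---|---|
| 0.02 | 81% | 90% | 91% | 93% |
| 0.05 | 23% | 62% | 69% | 80% |
| 0.10 | 0.03% | 9% | 16% | 41% |

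**5. What the two intervals look like.** Take, as an illustration only, n = 51, QALY SD 0.20, cost SD 1500, differences of 0.02 QALY and +500 in cost, uncorrelated, and a threshold of 50,000 per QALY. The SEs are 0.20 × √(2/51) = 0.0396 QALY and 1500 × √(2/51) = 297.
- Share of replicates at or below zero QALYs: Φ(−0.02/0.0396) = 31%.
- Percentile ICER interval by normal approximation: about −178,000 to +187,000 per QALY. One 1000-replicate bootstrap with the same means and SDs gave about −219,000 to +210,000, with 67% of replicates costlier and better, 29% costlier and worse, and the rest in the two cheaper quadrants.
- Net benefit: 50,000 × 0.02 − 500 = 500. Its SE is √((50,000 × 0.0396)² + 297²) = 2002, so the interval is 500 ± 3925, or about −3,400 to +4,400. It is wide, but every value in it has one meaning.
- The acceptability curve at that threshold would read Φ(500/2002) = 0.60 and would show nothing about size.

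**6. Baseline HUI3.** Under the same model the slope of QALY on baseline is 0.0417 + 0.9583 × rb. Adjusting would cut the SE by 7-12% (rb 0.3), 18-24% (0.5) or 37-41% (0.7), but by only 1-2% at rb 0.1.

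The documents conflict on timing. Section 2.1 refers to a pre-randomization score. Sections 4.5.1 and 6.1 put randomization 2-3 months before the procedure and baseline collection about 1 week before it. The appendix puts both in the −1 week column. Treatment is unmasked (Section 4.5.2). If knowledge of allocation shifted baseline HUI3 by an assumed 0.02 and left follow-up unchanged, the adjusted difference would move by 0.9583 × rb × 0.02 = 0.006-0.013 QALY, and the unadjusted one by 0.0417 × 0.02 = 0.001.

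**The case against.** The strongest reply is that Section 8.4 already covers most of the decision uncertainty. It plans intervals on the mean effects, the plane and acceptability curves. A curve built from joint replicates is the probability of positive net benefit at each threshold. That stands: a reader might infer that the economic analysis leaves uncertainty unquantified, and the documents do not support this. Nor is the percentile ICER interval invalid in coverage: in simulation under normal approximations it covered at 0.94-0.98, against 0.94-0.95 for net benefit. The problem is how it reads. What remains missing is a size of net benefit with limits.

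Further replies also stand:
- **Frequency.** A reader might infer that straddling is likely. That holds only if the true QALY difference is small, and the documents do not give one.
- **Missing detail.** A reader might fault the absence of a QALY formula, a named bootstrap interval type or an order for imputation and bootstrap. References 18, 23 and 24 are cited for method, and reference 30 is by its title a paper on bootstrap intervals for cost-effectiveness ratios. They cannot be seen here and may settle these points, so they are not part of this concern. Any figure for understated error from bootstrapping imputed data would also assume an analysis that the plan does not state.
- **Baseline HUI3.** A reader might infer that leaving it out is an error. The unadjusted QALY difference is unbiased over repeated trials. On the schedule in Sections 4.5.1 and 6.1, baseline is measured after unmasked allocation, and the unadjusted analysis is then the safer main one. The only correlation in the documents is 0.0, for MHQ in Section 8.2, so the precision gain is also uncertain.

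**Conclusion.** The concern holds as a low-cost improvement to a secondary analysis. The planned ordered interval on the ICER becomes unreadable whenever bootstrap QALY differences straddle zero, and an interval on net benefit from the same replicates does not have this fault. The frequencies in the table rest wholly on the assumed HUI3 SDs, correlations, trapezoid formula and true differences; none of these is in the documents. The planned plane and acceptability curves stay valid, and neither the primary MHQ analysis nor the sample size is touched.

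**What to change.** In Section 8.4:

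1. From the same 1000 replicates, report incremental net monetary benefit (threshold × QALY difference − cost difference) with a 95% interval at each threshold planned for the acceptability curves. In each replicate, estimate it by regressing patient-level net benefit on arm and joint type.
2. Give the ICER as a point estimate with the plane, in place of an ordered interval.
3. Also report a QALY difference adjusted for baseline HUI3. Reconcile Sections 2.1, 4.5.1 and 6.1 and the appendix on when baseline is measured relative to randomization. Make the adjusted analysis the main one only if HUI3 is confirmed to come before randomization; otherwise keep it as a sensitivity analysis and state that knowledge of allocation may have influenced the covariate.

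The cost is one extra reported analysis and a few sentences. Net benefit needs no new data and no added patients. Only a decision to move baseline HUI3 ahead of randomization would change the visit schedule, and items 1 and 2 do not depend on that.

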9 ETHICS/PROTECTION OF HUMAN SUBJECTS

9.1 Ethical Standard

The investigator will ensure that this study is conducted in full conformity with the principles set forth in Tri-Council Policy Statement-2: Ethical Conduct for Research Involving Humans (2010).

9.2 Research Ethics Board (REB)

The protocol, informed consent form(s), recruitment materials, and all subject materials will be submitted to the Research Ethics Board (REB) for review and approval.

Approval of both the protocol and the consent form must be obtained before any subject is enrolled. Any amendment to the protocol will require review and approval by the REB before the changes are implemented in the study.

9.3 Informed Consent Process

Informed consent is a process that is initiated prior to the individual agreeing to participate in the study and continues throughout study participation. Extensive discussion of risks and possible benefits of study participation will be provided to subjects and their families, if applicable. A consent form describing in detail the study procedures and risks will be given to the subject. Consent forms will be REB-approved, and the subject is required to read and review the document or have the document read to him or her. The investigator or designee will explain the research study to the subject and answer any questions that may arise. The subject will sign the informed consent document prior to any study-related assessments or procedures. Subjects will be given the opportunity to discuss the study with their surrogates or think about it prior to agreeing to participate. They may withdraw consent at any time throughout the course of the study. A copy of the signed informed consent document will be given to subjects for their records. The rights and welfare of the subjects will be protected by emphasizing to them that the quality of their clinical care will not be adversely affected if they decline to participate in this study.

The consent process will be documented in the clinical or research record.

Consent for the follow-up portion of the EXTEND trial will take the form of verbal consent over the telephone. The principal investigator's office administrator or the study coordinator will contact the patients to obtain consent using the script uploaded to the HiREB portal. The date that the patient was contacted, their consent decision and who obtained consent will be recorded on the form also uploaded to the HiREB portal.

10 DATA HANDLING AND RECORD KEEPING

10.1 Case Report Forms (CRFs)

Data will be recorded on study-specific paper-based CRFs by the site investigator or by designated staff authorized by the investigator and sent to the office of the principal investigator for central review and entry into the study database by the research assistant. The CRFs must be completed as soon as possible during or after any patient visit. Access to CRF data will be limited to personnel directly participating in the study. Data should be recorded on the CRF completely by the site investigator or by staff

authorized by the investigator. Completed CRFs will be shipped to the office of the PI by courier service.

10.2 Data Management Responsibilities

Paper-based CRFs and patient diary/quality of life questionnaires will be used for this study and managed centrally in the office of the principal investigator. Data collected will be reviewed and entered into the study database by the research assistant. Entered data will be statistically checked for coherency and outliers. Data from the patient diaries will be extracted and recorded on study CRFs by the research assistant. All CRF data and questionnaires will be stored in a locked cabinet in a locked office at each site.

Personal data shall be handled and processed in accordance with national legislation regulating privacy and data protection. When the database has been declared to be complete and accurate, the database will be locked. Any changes to the database after that time can only be made by written agreement between the PI and the study site investigator.

10.3 Archiving of Study Documents

The investigator at each study site must make arrangements to store the essential study documents, (as defined in Essential Documents for the Conduct of a Clinical Trial [ICH E6, Guideline for GCP]).

In addition, the investigator is responsible for archiving of all relevant source documents so that the study data can be compared against source data after completion of the study (e.g. in case of inspection from regulatory authorities).

The investigator is required to ensure the continued storage of the documents, even if the investigator, for example, leaves the clinic/practice or retires before the end of required storage period.

11 PUBLICATION PLAN

Findings will be shared and discussed with all of the investigators for the study. An estimated timeline for creation of an abstract/manuscript will be defined at that time. The publication or presentation of any study results shall comply with all applicable privacy laws.

Limited Palmar Fasciectomy (LPF)			X					
ASSESSMENTS:								
In-hospital utilization			X					
Baseline demographics		X						
HRQL questionnaires		X		X	X	X	X	
Range of Motion		X		X	X	X	X	
Resource utilization				X	X	X	X	X
AE/SAE monitoring				X	X	X	X	X
Recurrence				X	X	X	X	X
Study completion							X	X
